4.2 Anticipated Adverse Events

[figure not shown]
The following AEs and symptoms may be associated with the Calypso Knee System and/ or surgical procedure:

4.3 Subsequent Surgical Interventions of the Knee

- **Revision:** A revision is a procedure that adjusts or in any way modifies or removes *part* of the original implant configuration with or without replacement of a component. A revision may also include adjusting the position of the original configuration. This may include removing a component of the device and only replacing that single component.
- **Removal:** A removal is a procedure where all of the original system configuration is removed with or without replacement due to, for example, mechanical failure of the device, pain or infection.
- **Re-operation:** A reoperation is any surgical procedure that does not include removal modification, or addition of any components to the system (e.g., drainage of a hematoma at the surgical site).
- **Supplemental fixation:** A supplemental fixation is a procedure in which additional instrumentation not under study in the protocol is implanted.
- **Other interventions:** This category includes other surgeries of the study knee that the subject incurs while enrolled in the study that seemingly are unrelated to the implanted device.

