2.4 Study Endpoints

2.4.1 Primary Endpoint

The primary endpoint is a 24 month composite endpoint demonstrating non-inferiority of the Calypso Knee System to HTO data. A subject is a responder if all of the following components are met at 24 months:

- Clinically significant improvement of at least 20% from baseline on the WOMAC pain questions in the KOOS Knee questionnaire with a change of ≥ 10 points
- Clinically significant improvement of at least 20% from baseline on the WOMAC function questions in the KOOS Knee questionnaire with a change of ≥ 10 points
- Freedom from the following device-related serious adverse events:
 - deep infection requiring surgical intervention (Both arms)
 - damage to adjacent neurovascular or ligament structures necessitating reconstruction (Both arms)
 - non-union (HTO only)
- Maintenance of implant integrity as evaluated by radiographic assessment

NOTE: A subject will be considered a non-responder if they have a conversion to arthroplasty or loss of implant integrity of the Calypso Knee System at 24 months

Details of the radiographic assessment for implant integrity may be found in the Radiographic Evaluation Protocol (CLIN102792).

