5.1 Additional Outcomes

Safety Observations:

- Knee Range of Motion (ROM)
 - Measured passively defined as degrees of flexion and extension
- Adverse Events by type, over time, severity, seriousness, and relatedness
- Subsequent surgical interventions of the knee by type of surgical intervention (revision, removal, re-operation (includes conversion to arthroplasty) supplemental fixation, other intervention)
- Metal ion levels
- In the event of a Calypso Knee System removal, the following assessments will be evaluated:
 - Radiographic evaluations
 - MRI assessment as available
 - Calypso Knee System (implant) retrieval analysis
 - Histology
 - Metal Ion levels
 - Arthroplasty conversion data, if applicable

Effectiveness/Other Observations:

- Patient reported knee outcome measures and activity (KOOS Knee Survey, Activity Questionnaire, SF-12 Health Survey, Patient Satisfaction)
- Investigator reported KSS

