5.3 Follow-Up and Reporting

All subjects enrolled and devices used in the clinical study will be accounted for in the final report. All reasons for exclusion from analysis will be carefully documented. Similarly, for all subjects and devices included in an analysis population, the measurements of all important variables must be accounted for at all relevant time points. Additional information that is available on subjects screened for entry but not enrolled will also be summarized.

Subjects with early termination will be identified and a descriptive analysis of them provided, including the reasons for their loss to follow-up and known treatment outcome.

Subjects requiring removal of the Calypso Knee System will continue to participate in follow-up through the duration of the study. These subjects will take part in all protocol required follow up examinations, test, and the completion of questionnaires.

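### Conversion to arthroplasty is tabulated as a re-operation, a category that by definition excludes any explant, so the removal count can be too low

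*Combined protocol and SAP*

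**What the plan says.** Section 4.3 sets out five types of later knee surgery. Three matter here.

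- Re-operation: "A reoperation is any surgical procedure that does not include removal modification, or addition of any components to the system". The example given is draining a hematoma.
- Removal: "A removal is a procedure where all of the original system configuration is removed with or without replacement". Mechanical failure, pain and infection are given as example reasons.
- Revision: "A revision is a procedure that adjusts or in any way modifies or removes" part of the implant as first configured.

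Section 5.1 then lists the types by which interventions are to be reported: "revision, removal, re-operation (includes conversion to arthroplasty) supplemental fixation, other intervention". The Protocol Summary repeats this list twice, under the safety observations and under the analysis of additional observations. None of the three lists makes an exception for a conversion in which the implant is taken out.

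Section 5.1 also lists what is to be evaluated when a device is removed, and one item is "Arthroplasty conversion data, if applicable". Section 5.3 adds: "Subjects requiring removal of the Calypso Knee System will continue to participate in follow-up through the duration of the study". For the primary endpoint, Section 2.4.1 handles conversion directly: "A subject will be considered a non-responder if they have a conversion to arthroplasty".

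**The concern.** The definitions and the reporting lists assign the same operation to different rows. If the Calypso system is explanted during a conversion, the definitions make the operation a removal and the lists make it a re-operation. Interventions by type are a listed safety observation in a pivotal implant study, and the removal row is where a reader looks to see how often the device had to come out. Under the label as written, a conversion with explant can be placed beside hematoma drainage and left out of the removal row. The published table would not show whether the same operation had also been counted as a removal, and different coders could reasonably choose differently.

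**Working it through.** The plan states no removal, re-operation or conversion rate, so there is no figure to reproduce. The check compares the definitions with the lists and then works out the weight of one event.

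**Inputs**

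- Definitions of re-operation, removal and revision: Section 4.3.
- Reporting lists: Section 5.1 and the Protocol Summary (two places).
- Planned enrolment, 80 subjects: Section 2.1.1.
- Number of explants at conversion: not given. A range of 1 to 5 is assumed for illustration only.

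**Step 1: apply each rule to each form of conversion**

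| Conversion to arthroplasty | Row by Section 4.3 definitions | Row by the reporting lists | Conflict? |
|---|---|---|---|
| Whole system taken out at the same operation | Removal | Re-operation | Yes |
| Part of the system taken out at the same operation | Revision | Re-operation | Yes |
| System already removed at an earlier operation | Re-operation is possible, since no component is left to take out | Re-operation | No |

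**Step 2: does the plan foresee the conflicting case?** The assessments triggered by a device removal include arthroplasty conversion data. That item could also cover a later conversion in a subject who stays in follow-up under Section 5.3. Nothing limits it to that, and an explant during the conversion fits it directly.

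**Step 3: size per event.** With n = 80 and one event per subject, each event carries 1/n = 1/80 = 1.25 percentage points.

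| How a full explant at conversion is coded | Error in Removal, per event | Error in Re-operation, per event |
|---|---|---|
| (a) Re-operation only | 1.25 points too low | 1.25 points too high |
| (b) Both rows | 0 | 1.25 points too high by its own definition |
| (c) Removal only | 0 | 0, but the label's statement that conversions are included is then untrue |

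For a partial explant, the row that falls short under (a) is Revision.

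**Step 4: range.** For k events under (a), the removal rate is understated by k/80. For k = 1 this is 1/80 = 1.25 points; for k = 5 it is 5/80 = 6.25 points. Under (b) the understatement is 0 for any k. A conversion after an earlier removal adds no error to either row.

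**The case against.** The strongest reply is that the undercount needs a rule the plan does not state, namely that each operation goes in one row only. If the types may overlap, an explant at conversion is still counted as a removal. Listing conversion data among the removal assessments points that way, because it treats the event as a removal that carries conversion information. Section 5.3 also requires every subject and device to be accounted for in the final report, and a removal triggers retrieval analysis, histology and other assessments, so the explant would not be lost from the record. A counting rule may also exist in redacted text or in documents not supplied, such as the events committee charter.

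Much of this stands. The removal undercount is conditional on single coding, the explant should be traceable elsewhere, and the damage is confined to descriptive safety tables. Neither the primary endpoint nor the five secondary endpoints (time to full weight bearing and WOMAC changes) use this classification. It is also fair that the assumed 1 to 5 events do not come from the plan, and that 80 need not be the number implanted, since Appendix A defines enrolment by the start of anesthesia.

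It does not remove the problem. Overlapping categories would repair the removal row, but an operation that takes the implant out still could not be a re-operation under Section 4.3. A rule in another document would leave the definitions and the three lists in conflict.

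**Conclusion.** The concern holds. Section 4.3 and the reporting lists contradict each other for any conversion at which the system is taken out in whole or in part. The contradiction is plain on the text and needs no assumption about what is redacted. The size does rest on assumptions: each full explant at conversion that is coded only as a re-operation understates the removal rate by 1.25 points on a denominator of 80 (slightly more if fewer are implanted), which gives 1.25 to 6.25 points for an assumed 1 to 5 events. The removal understatement is 0 if the event is coded in both rows, although the re-operation row is then wrong by its own definition. The consequence is limited to the safety table of interventions by type. It should be corrected before that table is produced, so that coding cannot depend on the results.

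**What to change.** - Delete the parenthesis that places conversion to arthroplasty under re-operation, in Section 5.1 and in both places in the Protocol Summary. The list in Section 2.4.3 breaks off in the public copy; if it carries the same label, change it there too.
- Report conversion to arthroplasty on its own row.
- When the system is explanted at the same operation, also count that operation under Removal if all of it is taken out, or under Revision if only part is.
- State in Section 4.3 whether one operation may be counted under more than one type. The same sentence should say whether implanting arthroplasty components counts as supplemental fixation, since the wording of that definition could be read to include it.

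This changes reporting only. The cost is a wording change in Section 4.3, Section 5.1 and the Protocol Summary, plus one table row. No new data should be needed as long as the operative record shows what was taken out; the data-collection sections are redacted, so this should be confirmed. The reported removal rate may be higher as a result.

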4.4 Device Malfunction

All device malfunctions of the Calypso Knee System must be reported within 24 hours of the knowledge of the event in the EDC system.

5.0 STATISTICAL ANALYSIS PLAN

Refer to the Statistical Considerations and Preliminary Propensity Score (PS) Design Memorandum (CLIN103113) for the Calypso Clinical Study for primary and secondary endpoint study analysis, analysis population, sample size and power, evaluation of missing data, and baseline covariates against endpoint success rates.

5.1 Additional Outcomes

Safety Observations:

- Knee Range of Motion (ROM)
 - Measured passively defined as degrees of flexion and extension
- Adverse Events by type, over time, severity, seriousness, and relatedness
- Subsequent surgical interventions of the knee by type of surgical intervention (revision, removal, re-operation (includes conversion to arthroplasty) supplemental fixation, other intervention)
- Metal ion levels
- In the event of a Calypso Knee System removal, the following assessments will be evaluated:
 - Radiographic evaluations
 - MRI assessment as available
 - Calypso Knee System (implant) retrieval analysis
 - Histology
 - Metal Ion levels
 - Arthroplasty conversion data, if applicable

Effectiveness/Other Observations:

- Patient reported knee outcome measures and activity (KOOS Knee Survey, Activity Questionnaire, SF-12 Health Survey, Patient Satisfaction)
- Investigator reported KSS

5.2 Baseline Variables

Demographic and baseline variables will be summarized. Sample sizes, means, standard deviations and ranges will be presented for all continuous variables.

5.3 Follow-Up and Reporting

All subjects enrolled and devices used in the clinical study will be accounted for in the final report. All reasons for exclusion from analysis will be carefully documented. Similarly, for all subjects and devices included in an analysis population, the measurements of all important variables must be accounted for at all relevant time points. Additional information that is available on subjects screened for entry but not enrolled will also be summarized.

Subjects with early termination will be identified and a descriptive analysis of them provided, including the reasons for their loss to follow-up and known treatment outcome.

Subjects requiring removal of the Calypso Knee System will continue to participate in follow-up through the duration of the study. These subjects will take part in all protocol required follow up examinations, test, and the completion of questionnaires.

6.0 STUDY MANAGEMENT

6.1 Sponsor Ethical and Regulatory Considerations

[REDACTED]

General Duties

[REDACTED]

[REDACTED]

Selection of Clinical Sites

[REDACTED]

[REDACTED]

Site Training

[REDACTED]

[Redacted]

Investigator Training

[Redacted]

[Redacted]

Subject Confidentiality

[Redacted]

[Redacted]

Data Management

[Redacted]

Record Retention

[Redacted]

[Redacted text block]

6.2 Investigator Responsibilities

[Redacted text block]

[Redacted text block]

6.2.1 IRB Approval and Informed Consent

[Redacted text block]

[Redacted text block]

[Redacted text block]

[Redacted text block]

[REDACTED]

6.2.2 Data Collection and Reporting

[REDACTED]

[REDACTED]

6.2.3 Data Completion and Submission

[REDACTED]

[REDACTED]

6.2.4 Device Accountability

[REDACTED]

6.2.5 Source Documents

[REDACTED]

- [REDACTED]

- [REDACTED]

[REDACTED]

6.2.6 Regulatory Filing

[REDACTED]

[REDACTED]

[REDACTED]

6.2.7 Audits/Inspections

[REDACTED]

6.3 Clinical Events Committee (CEC)

An independent Clinical Events Committee (CEC) will be established to adjudicate all serious adverse events

[REDACTED]

[REDACTED]

[REDACTED]

6.4 Medical Monitoring

[REDACTED]

- [REDACTED]

6.5 Protocol Deviations

[REDACTED]

[REDACTED]

- [REDACTED]

2. Risks associated with knee surgery include:

- [REDACTED]

- [REDACTED]

[REDACTED]

3. Risks associated with Calypso Knee System:

- [REDACTED]

[REDACTED]

Risks Associated with Radiographs

[REDACTED]

[REDACTED]

Risks Associated with MRI

[REDACTED]

Reproductive Risks

[REDACTED]

Metal Ion Blood Draw Risks

[REDACTED]

Allergy Risks

[REDACTED]

7.2 Minimizing Study Risks

[REDACTED]

- | [REDACTED]
- | [REDACTED]
- | [REDACTED]
- | [REDACTED]

- [REDACTED]
- [REDACTED]
- [REDACTED]
- [REDACTED]
- [REDACTED]

7.3 Benefit-Risk Summary

[REDACTED]

7.4 Anticipated Changes during the Investigation

There are no known anticipated changes of the Calypso Knee System during the investigation.

8.0 MONITORING PLAN

[REDACTED]

[REDACTED]

Site Qualification/Initiation Visits

[REDACTED]

[REDACTED]

Interim Monitoring Visits

[REDACTED]

[REDACTED]

[REDACTED]

Site Close Out Visit

[REDACTED]

Qualifications of Study Monitor

[REDACTED]

APPENDIX A: DEFINITIONS

ANALGESIC

A pain-relieving effect with no loss of consciousness

BLEEDING COMPLICATION

A procedure related hemorrhagic event that requires a transfusion or surgical repair.

BURSITIS

Bursitis is an inflammation of the native bursae that can result in irritation and pain.

CELLULITIS

A superficial, spreading infection of the skin and subcutaneous tissue, usually following lacerations and surgical wounds. The most common causative organism is penicillin sensitive streptococci. Cellulitis is characterized by signs of inflammation (local pain, tenderness, swelling and erythema). The border between involved and uninvolved skin is usually indistinct and systemic illness characterized by fever, chills, malaise and toxicity is frequently present.

<http://www.who.int/surgery/publications/en/SCDH.pdf>

DEEP VEIN THROMBOSIS

Deep vein thrombosis (DVT) is a blood clot that forms in a vein deep in the body.

Http://www.nhlbi.nih.gov/health/dci/diseases/dvt/dvt_what.html

DEVICE MALFUNCTION

The failure of a device to meet its performance specifications or otherwise perform as intended.

Performance specifications include all claims made in the labeling for the device. (21 CFR Part 803)

DIABETES MELLITUS

A condition caused by insufficient production of insulin resulting in abnormal metabolism of carbohydrates, fats and protein. Diabetes mellitus is defined as symptoms of hyperglycemia (thirst, polyuria, weight loss, visual blurring) and a casual plasma glucose concentration of ≥ 200 mg/dl; or a fasting plasma blood glucose concentration of ≥ 126 mg/dl; or a 2-hour post load glucose ≥ 200 mg/dl during an oral glucose tolerance test as described by the World Health Organization (WHO).

ENROLLED

Subjects who sign informed consent and undergo an anesthesia start time for purposes of receiving the Calypso Knee System.

HEMATOMA

A localized mass of extravasated blood that is relatively or completely confined within an organ or tissue, a space, or a potential space that measures four centimeters or greater in diameter at the vascular access site, or those requiring transfusion or necessitating prolonged hospitalization.

HEMORRHAGE

An escape of blood through ruptured, or unruptured vessel walls.

KNEE SCARRING, ARTHROFIBROSIS, OR PERIPROSTHETIC LOCAL ADHESIONS

A process of fibrosis or proliferation of fibrotic tissue as part of the healing process. May occur about the knee joint, intra-articular or extra-articular or present as periprosthetic local adhesions. Arthrofibrosis is a term typically used when the knee scarring is excessive and limiting ROM.

LIFE THREATENING

The subject is or subject was, in the view of the investigator, at immediate risk of death from the adverse event as it occurred. It does not include an adverse event that, had it occurred in a more severe form, might have caused death.

LOCAL INFLAMMATION

A local protective tissue response to injury or destruction of tissues, which serves to destroy, dilute, or wall off both the injurious agent and the injured tissues. The classical signs of acute inflammation are pain, heat, redness, swelling, and loss of function. [http://medical-dictionary.thefreedictionary.com/systemic+inflammation+response+syndrome+\(SIRS\)](http://medical-dictionary.thefreedictionary.com/systemic+inflammation+response+syndrome+(SIRS))

MISSED ENROLLMENT

Subjects who do meet inclusion/exclusion criteria but were in the screening process when enrollment closed.

NEURALGIA

Pain in one or more nerves that occurs without stimulation of pain receptor (nociceptor) cells. Neuralgia pain is produced by a change in neurological structure or function rather than by the excitation of pain receptors that causes nociceptive pain. <http://en.wikipedia.org/wiki/Neuralgia>

PATIENT REPORTED OUTCOME MEASURES (PROMS)

- **KOOS:** The Knee injury and Osteoarthritis Outcome Score (KOOS) Knee Survey is a disease-specific, measure of 5 subscales; Pain, other Symptoms, Function in daily living (ADL), Function in sport and recreation (Sport/Rec) and knee related Quality of life QOL. The last week is taken into consideration when answering the questions. KOOS Knee Survey contains the full and original version of the Western Ontario and McMaster's University Osteoarthritis Index (WOMAC) and thus WOMAC scores can be calculated from the KOOS Knee questionnaire. It is estimated to take about 10 minutes to complete the KOOS Knee questionnaire. <http://www.koos.nu/>
- **KSS:** Knee Society Score⁸⁷ is a standard clinical evaluation system for reporting results for subjects undergoing knee implant surgery and is both subject and physician derived (Scuderi et al). The new Knee Society Scoring System, copyrighted in 2011, is a validated system that combines an objective physician-derived component with a subjective patient-derived component. The objective knee score, completed by the surgeon, includes an assessment of alignment, ligament stability, and ROM along with deductions for flexion contracture or extensor lag. Given the diverse activity profiles of many contemporary subjects, the functional component of the score was improved to include a subject specific survey, which evaluates features such as standard activities of daily living, subject-specific sports and recreational activities (function), subject satisfaction, and subject expectations. Portions of the original Knee Society Clinical Rating System have been integrated into the new version to maintain the integrity of the prior version of the Knee Society score.
- **SF-12:** SF-12[®] Health Survey is a registered trademark of Medical Outcomes Trust. It is a short form of SF-36 in which it is 12 questions from each of the 8 concepts from SF-36 – split into physical health and mental health.
- **Subject Activity and Satisfaction:** Moximed generated questionnaire to capture level of subject activity and subject satisfaction post index procedure.
- **WOMAC:** The Western Ontario and McMaster Universities Arthritis (WOMAC) Index is self-administered, validated assessment of the three dimensions of pain, disability and joint stiffness in knee and hip osteoarthritis using a battery of 24 questions. <http://www.auscan.org/womac/index.htm>

PHYSICIAN REPORTED OUTCOME MEASURES

- **KSS:** Knee Society Score⁸⁷ is a standard clinical evaluation system for reporting results for subjects undergoing knee implant surgery and is both subject and physician derived (Scuderi et al). The new KSS survey has recently been validated by the Knee Society. It is both physician and subject derived. The objective knee score, completed by the surgeon, includes an assessment of alignment, ligament stability, and ROM along with deductions for flexion contracture or extensor lag. Subjects then record their VAS score of pain walking on level ground and on stairs or inclines satisfaction, functional activities, and expectations. Given the diverse activity profiles of many contemporary subjects, the functional

component of the score was improved to include a subject specific survey, which evaluates features such as standard activities of daily living, subject -specific sports and recreational activities, subject satisfaction, and subject expectations. Portions of the original Knee Society Clinical Rating System have been integrated into the new version to maintain the integrity of the prior version of the Knee Society score.

- **Pain:** Moximed generated questionnaire to capture confounding factors, type, location, and scale of pain.

PERONEAL NERVE INJURY

Damage to the peroneal nerve leading to loss of movement or sensation in the foot and leg. Injury may result in a loss of sensation, muscle control, muscle tone, and eventual loss of muscle mass because of lack of nervous stimulation to the muscles.

<http://www.ncbi.nlm.nih.gov/pubmedhealth/PMH0001795/>

SCREEN FAILURE

Subjects who sign informed consent but failed to meet one or more of the Inclusion/Exclusion criteria.

SOFT TISSUE IRRITATION

Superficial Tissue Irritation An inflammatory condition of superficial layers of the skin as a result of an aseptic irritant, such as skin reaction to suture or dressings.

Periprosthetic Soft Tissue Irritation An inflammatory condition of the tissues about the implant resulting from aseptic tissue irritation. Fluid may accumulate in the periprosthetic tissues possibly resulting in the tissue swelling, localized tenderness, pain and/or joint motion is restriction.

SYNOVITIS

An inflammatory condition of the synovial membrane of the knee joint as the result of aseptic trauma, often caused by extreme or excessive activity on the joint. The knee joint is swollen, tender, and painful; and motion is restricted

SURGICAL SITE INFECTION⁹⁰

Superficial Infection (skin and subcutaneous tissue) occurs after the operation *and* infection involves only skin or subcutaneous tissue of the incision *and* at least *one* of the following:

1. Purulent drainage, with or without laboratory confirmation, from the superficial incision.
2. Organisms isolated from an aseptically obtained culture of fluid or tissue from the superficial incision.
3. At least one of the following signs or symptoms of infection: pain or tenderness, localized swelling, redness, or heat *and* superficial incision are deliberately opened by surgeon, *unless* incision is culture-negative.

4. Diagnosis of superficial incisional SSI by the surgeon or attending physician.

Do *not* report the following conditions as SSI:

1. Stitch abscess (minimal inflammation and discharge confined to the points of suture penetration).
2. Incisional SSI that extends into the fascial and muscle layers (see deep incisional SSI).

Deep Incisional Infection (deep soft tissue, fascia and muscle)

Infection occurs if infection involves deep soft tissues (e.g., fascial and muscle layers) of the incision *and* at least *one* of the following:

1. Purulent drainage from the deep incision but not from the space component of the surgical site.
2. A deep incision spontaneously dehisces or is deliberately opened by a surgeon when the subject has at least one of the following signs or symptoms: fever ($>38^{\circ}\text{C}$), localized pain, or tenderness, unless site is culture-negative.
3. An abscess or other evidence of infection involving the deep incision is found on direct examination, during reoperation, or by histopathologic or radiologic examination.
4. Diagnosis of a deep incisional SSI by a surgeon or attending physician.

Notes:

1. Report infection that involves both superficial and deep incision sites as deep incisional SSI.
2. Report an organ/space SSI that drains through the incision as a deep incisional SSI.

Organ or Space Infection

Infection occurs if no implant is left in place or if implant is in place and the infection appears to be related to the operation *and* infection involves any part of the anatomy (e.g., organs or spaces), other than the incision, which was opened or manipulated during an operation *and* at least *one* of the following:

1. Purulent drainage from a drain that is placed through a stab wound[‡] into the organ/space.
2. Organisms isolated from an aseptically obtained culture of fluid or tissue in the organ/space.
3. An abscess or other evidence of infection involving the organ/space that is found on direct examination, during reoperation, or by histopathologic or radiologic examination.
4. Diagnosis of an organ/space SSI by a surgeon or attending physician.

Wound infections have been subdivided according to the following clinically related subgroups:

- **Aetiology:** In a primary infection, the wound is the primary site of infection, whereas a secondary infection arises following a complication that is not directly related to the wound;
- **Time:** An **Early** infection presents within 30 days of a surgical procedure, whereas an infection is described as **Intermediate** if it occurs between one and three months afterwards and **Late** if it presents more than three months after surgery;
- **Severity:** a wound infection is described as **Minor** if there is a discharge without cellulitis or deep tissue destruction, and **Major** if the discharge of pus is associated with tissue breakdown, partial or total dehiscence of the deep fascial layers of the wound, or if systemic illness is present.
